5.6.2.1. Clinical Laboratory Tests

Clinical laboratory tests will be displayed for the participants included in the safety analysis set.

Descriptive statistics will be presented for all chemistry, hematology, and urinalysis (pH and specific gravity) laboratory tests at scheduled time points in the double-blind and open-label phases.

Change from their respective baselines to each scheduled time point in the double-blind and openlabel phases will be summarized for chemistry, hematology, and urinalysis (pH, and specific gravity) tests and displayed by treatment group.

Abnormality criteria based on normal ranges will be applied to baseline and postbaseline values.

Postbaseline abnormalities will be compared with their corresponding baseline result:

- For abnormalities based on normal range and/or criteria: If the postbaseline value is above the upper limit and the baseline value is below the upper limit (eg, Normal or Low), then the postbaseline abnormality will be considered TE. The same applies to the postbaseline value being below the lower limit with the baseline value being above the lower limit (eg, Normal or High).
- If the baseline value is missing, a postbaseline abnormality will always be considered as TE. Number and percentage of participants with markedly abnormal postbaseline values in the double-blind and open-label phases will be presented by treatment group over time. A listing of TE laboratory values will be provided.

Shift tables will be provided for the double-blind and open-label phases summarizing the shift in laboratory values from baseline over time with respect to abnormality criteria (low, normal, high).

5.6.2.2. Vital Signs and Physical Examination Findings

Vital sign parameters including temperature (oral or tympanic), pulse and blood pressure (systolic and diastolic) will be summarized at each assessment timepoint for the double-blind and openlabel phases. Body Mass Index will be calculated as weight (kg)/(height (m))², at each time point that body weight is measured. The height measurement collected at screening will be used in the calculation. Descriptive statistics (N, mean, standard deviation, median, minimum and maximum) and change from the respective baselines will be summarized for the double-blind and open-label phases by treatment group at each scheduled visit.

Abnormality criteria (based on criteria defined below) will be applied to baseline and postbaseline values in the double-blind and open-label phases. For baseline values, increase or decrease criteria are not applied.

Postbaseline values will be considered TE if they meet both value and change criteria in the table below.

For criteria that do not include an increase or decrease from baseline for both double-blind and open-label phases:

- TE will be concluded if the postbaseline value is above the upper limit and the baseline value is below the upper limit (eg, Normal or Low). The same applies to the postbaseline value being below the lower limit with the baseline value being above the lower limit (eg, Normal or High).
- If the baseline value is missing, a postbaseline abnormality will always be considered as TE.

Incidence of treatment-emergent clinically important abnormalities in vital signs during the double-blind phase, as defined in Table 3, will be summarized for participants who had a baseline assessment and at least 1 postbaseline assessment for that vital sign.

Vital Sign	Criteria
Pulse	>100 bpm and with >30 bpm increase from baseline
	<50 bpm and with >20 bpm decrease from baseline
Systolic blood pressure	>140 mm Hg and with >40 mm Hg increase from baseline
	<90 mm Hg and with >30 mm Hg decrease from baseline
Diastolic blood pressure	>90 mm Hg and with >30 mm Hg increase from baseline
	<50 mm Hg and with >20 mm Hg decrease from baseline
Temperature	>38°C and with >=1°C increase from baseline

Table 3: Clinically Important Abnormalities in Vital Signs

A listing of participants with treatment-emergent clinically important abnormalities in vital signs will be presented, along with a listing of all vital sign measurements.

In addition, a by-subject listing of the physical examination data, neurological examination data and Brief neurological data will be presented.

5.6.2.3. Electrocardiogram

At screening a triplicate ECG is required where the mean values of ECG parameters will be used for entry into the eCRF. At all other visits, single twelve-lead ECG will be recorded. The screening ECG values are the last available ECG measurements before dosing and will therefore be used as the baseline values. The ECG parameters that will be analyzed are heart rate, PR interval, RR interval, QRS interval, QT interval, and corrected QT (QTc) interval using the following correction methods: Bazett's formula (QTcB), Fridericia's formula (QTcF).

Bazett's formula: QTcB (msec) = QT (msec) / (RR (msec)/1000)^{1/2}; if RR is missing, use QT (msec) * (HR(bpm)/60)^{1/2};

Fridericia's formula: QTcF (msec) = QT (msec) / (RR (msec)/1000)^{1/3}; if RR is missing, use QT (msec) * (HR(bpm)/60)^{1/3};

The number and percentage of participants with QTc interval will be summarized at each scheduled time point for each treatment phase (double-blind and open-label) by treatment group. The number and percentage of participants with QTc interval increases from baseline to the maximum postbaseline value will be summarized for double-blind and open-label phases by treatment group. Refer to the following table for summary categories.

Criteria for Abnormal QTc Values and Changes From Baseline					
Clinically Significant QTc	No	≤500			
Value	Yes	>500			
QTc change from baseline	No concern	≤30			
(msec)	Concern	>30 to ≤60			
	Clear concern	> 60			
QTc value (msec)	Normal QTc	≤450 for male, ≤470 for female			
		>450 to ≤480 for male, >470 to ≤480 for female			
		>480 to \(\leq 500\)			
		>500			
These criteria are based on the ICH E14 Guideline					

A shift table will be provided summarizing the shift from baseline to maximum QTc interval classification through the double-blind phase.

Descriptive statistics of ECG parameters and change from baseline will be summarized by treatment group at each scheduled visit for double-blind and open-label phases

If ECG measurements are repeated at a visit, they will be averaged. The averaged value will be considered the 'Visit' ECG result.

Abnormality criteria (based on criteria defined below) will be applied to baseline and postbaseline values.

Postbaseline abnormalities will be compared with their corresponding baseline result:

- TE will be concluded if the postbaseline value is above the upper limit and the baseline value is below the upper limit (e.g., Normal or Low). The same applies to the postbaseline value being below the lower limit with the baseline value being above the lower limit (eg, Normal or High).
- If the baseline value is missing, a postbaseline abnormality will always be considered as TE.

The number and percentage of participants with treatment-emergent ECG values and abnormal postbaseline values (relative to baseline) will be presented by treatment group over time for each phase of the study:

- Heart rate (bpm): <45 and >100
- PR interval (msec): <120 and >200
- QRS interval (msec): >120
- OTc (msec): >470 in women and >450 in men

The interpretation of the ECGs will be displayed by the number and percentage of participants meeting the normality criteria. The interpretation will be summarized over time by the two intervention phases.

A listing of clinically relevant ECG abnormalities will also be provided.

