#### Footnotes:

- a) If a participant discontinues treatment before the end of the double-blind treatment period, early withdrawal (EW) visit should be completed
- b)  $\pm 2$  days
- c) When required for practical reasons, the baseline period may be up to 1 week longer or shorter than 8 weeks. Baseline monthly seizure count will be defined as the number of observable focal onset seizures recorded during the baseline period, multiplied by 28/XBL, where XBL is the number of days comprising the baseline.
- d) Participant should come to the study visit in fasted conditions (at least 4 hours) when possible
- e) Visit in the morning hours before noon.
- f) Participants will be contacted by phone during the baseline period to confirm correct use of the e-diary. This contact should take place at least 4 weeks after the start of the baseline period, but multiple contacts are allowed when required.
- g) After completion of all visit assessments (except post-dose PK blood sample).
- h) Except in-clinic doses during visits
- i) To be collected before dosing and when possible in fasting condition
- j) During Visit 2, also collect a blood sample for biomarkers at 2 hours post dose (together with PK-sample)
- k) Collect with clinical laboratory sample.
- l) Detailed timepoints for PK sample collection are provided in Table 4: PK sampling Strategy
- m) Only levetiracetam or brivaracetam and JNJ-40411813, at EW only when EW visit is after Visit 6.
- n) CCI
- o) Only seizure counts. Only subjects who continued treatment to the end of the double-blind treatment period (Week 12) or have completed the study as per Section 7.2
- p) CCI
- q) Systolic and diastolic blood pressure, heart rate and body temperature (oral or tympanic)
- r) Triplicate ECG at screening. Single ECG at the other timepoints.
- s) In women of childbearing potential only. Serum pregnancy test at screening and a urine pregnancy test at the other visits.

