# 7.3. Participant Discontinuation/Withdrawal from the Studya

A participant will be withdrawn from the study for any of the following reasons. The participant must discontinue the study intervention and, whenever possible, the early withdrawal visit must be completed.

Lost to follow-up

-

<sup>a This section has been amended by Amendment INT-2

- Death
- Withdrawal of consent. When a participant withdraws consent, effort should be made to determine if the cause of withdrawal was due to tolerability or lack of efficacy.
- Noncompliance to take the study intervention. Noncompliance will be decided on a case-by-case basis depending on the number of missed tablets and the interval between missed doses.
- Experiences a severe adverse event or serious adverse event (SAE) while receiving treatment, that is considered at least possibly related to study drug.
- The investigator or sponsor believes (e.g., that for safety or tolerability reasons such as a SAE at least possibly related to the study intervention) it is in the best interest of the participant to discontinue the study intervention.
- A participant who shows signals of clinically meaningful acute suicidal ideation at any time during the study should be withdrawn from the study and promptly referred for appropriate medical/psychiatric care.
- The participant becomes pregnant.
- If the QTcF interval is higher than 500 msec or is prolonged >60 msec from the baseline (Screening) value. If the QTcF is not readily available, the QTcB may be used instead. The participant will continue to be monitored (maximum 12 hours) by repeated 12-lead ECGs (at least every 60 minutes) until the ECG normalizes.
- If the liver function tests exceed the values as presented in Section 11.7.

When a participant withdraws before completing the study, the reason for withdrawal is to be documented in the eCRF and in the source document. Study intervention assigned to the withdrawn participant may not be assigned to another participant.

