#### **ECG**

Heart rate and ECG intervals (RR, PR, QRS and QT) as well as corrected QT intervals according to Bazett's formula (QTcB) and Fridericia's formula (QTcF) (Bazett 1920, Sagie 1992, Hodges 1983, International Conference on Harmonization [ICH] 2005) from the 12-lead ECG will be summarized at baseline (Screening) and at each scheduled time point and for changes from baseline using descriptive statistics.

The number and percentage of participants with at least one occurrence of a treatment-emergent potentially clinically important QTc measurement (QTc value >450, >480, or >500 msec) or with a change from baseline in QTc>30 msec or 60 msec, will be summarized by treatment group.

Data listings of participants with any potentially clinically important values or with a change from baseline in QTc will be provided.

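### Averaging ECGs repeated at a visit can move a participant out of the QTc >500 msec category, and the open-label phase has no ever-reached count

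*SAP*

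**What the plan says.** The Schedule of Activities (Protocol 1.2, footnote r) sets the recordings: "Triplicate ECG at screening. Single ECG at the other timepoints". SAP 5.6.2.3 agrees, so the screening triplicate is the only planned replicate.

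Protocol 7.3 withdraws a participant whose QTcF exceeds 500 msec or rises more than 60 msec above screening, and adds: "The participant will continue to be monitored (maximum 12 hours) by repeated 12-lead ECGs (at least every 60 minutes) until the ECG normalizes".

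SAP 5.6.2.3 then gives a general rule: "If ECG measurements are repeated at a visit, they will be averaged. The averaged value will be considered the 'Visit' ECG result". It does not distinguish repeats by their reason.

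Three QTc summaries in the same section could use that result:

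- Value categories, with cut-points at 450 (men) or 470 (women), 480 and 500 msec: "The number and percentage of participants with QTc interval will be summarized at each scheduled time point for each treatment phase".
- Change categories (>30 and >60 msec), based on "QTc interval increases from baseline to the maximum postbaseline value will be summarized for double-blind and open-label phases by treatment group".
- A shift table: "A shift table will be provided summarizing the shift from baseline to maximum QTc interval classification through the double-blind phase".

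Protocol 9.4 asks for something different. It wants the number and percentage of "participants with at least one occurrence of a treatment-emergent potentially clinically important QTc measurement", with limits at 450, 480 and 500 msec. It also promises listings: "Data listings of participants with any potentially clinically important values or with a change from baseline in QTc will be provided". Protocol 10.7 and 10.9.4 carry Sections 7.3 and 9.4 into the open-label phase.

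**The concern.** Averaging suits planned replicates, but after screening there are none. Postbaseline, the rule can act only on unplanned repeats, and the one sequence the protocol requires is started by a high QTc and continued until it comes down. Averaging those tracings with the reading that triggered them dilutes the event that the >500 category exists to count.

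At stake is whether the tables report every participant who reached the value that triggers withdrawal. The by-timepoint count can miss such a participant. In the double-blind phase the shift table recovers the case only if its maximum is a single reading, which the SAP does not say. If the maximum is taken over visit means, no SAP table shows the case. In the open-label phase there is no shift table, so the >480 and >500 msec values appear only by time point on either meaning of maximum. Protocol 10.2.1 describes this as the first study with exposure beyond 3 months.

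**Working it through.** The plan states no figure to reproduce, and the documents give no on-study QTc values. All readings below are assumed. Protocol 7.3 does not define normalisation; it is taken here as the SAP's normal limit (≤470 msec for women, ≤450 msec for men).

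**Two worked cases**

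- Woman: (512 + 486 + 462)/3 = 486.7 msec, category >480 to ≤500.
- Man: (512 + 486 + 462 + 448)/4 = 477.0 msec, category >450 to ≤480.
- Highest single reading in both: 512 msec, category >500.

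**Break-even**

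A first reading of 500 + d followed by k repeats leaves >500 when the mean of the repeats is at or below 500 − d/k. With one repeat and first reading F, this means a repeat at or below 1000 − F:

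| First reading F | Leaves >500 if the one repeat is at most |
|---|---|
| 505 | 495 |
| 512 | 488 |
| 520 | 480 |
| 530 | 470 |
| 550 | 450 |

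**Range: linear fall, hourly repeats, stopping at the normal limit or after 12 repeats**

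With a fall of r msec per hour and k repeats, the mean is F − r·k/2.

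| Start | Fall per hour | Woman: repeats, mean | Man: repeats, mean |
|---|---|---|---|
| 512 | 1 | 12, 506.0 (stays >500) | 12, 506.0 (stays >500) |
| 512 | 2 | 12, 500.0 (leaves) | 12, 500.0 (leaves) |
| 512 | 5 | 9, 489.5 (leaves) | 12, 482.0 (leaves) |
| 512 | 10 | 5, 487.0 (leaves) | 7, 477.0 (leaves) |
| 550 | 10 | 8, 510.0 (stays >500) | 10, 500.0 (leaves) |

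**Effect on the table**

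In an active arm of 40 (the planned size in Protocol 9.1), one moved participant changes the >500 cell from 1/40 = 2.5% (exact 95% CI 0.1 to 13.2%) to 0/40 = 0% (0 to 8.8%).

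**Change categories, only if the maximum is taken over visit means**

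With an assumed screening value of 428 msec, the single-reading change is 512 − 428 = +84. Using the means, it is 486.7 − 428 = +58.7 (woman) or 477.0 − 428 = +49.0 (man). Both leave >60.

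**If the repeats are stored as separate visits**

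SAP 5.1.1 uses the visit closest to the target day and, for equidistant visits, the later one. Same-day repeats are equidistant, so the by-timepoint table would take the later reading, which is normally lower. The section lets unused visits count towards clinically important endpoints, but the SAP never says that the QTc categories are such endpoints.

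**Open-label phase**

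The SAP sentence on the maximum names both phases but covers increases from baseline only. The shift table is limited to the double-blind phase. The abnormality table that closes the section uses only >470 (women) and >450 (men), over time. Nothing counts participants who ever exceeded 480 or 500 msec.

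**The case against.** The strongest objection is that the mechanism depends on storage. Protocol 7.3 describes monitoring of a participant who is already being withdrawn, and neither document says those tracings belong to a scheduled visit. Held as unscheduled records outside the visit structure, they would leave the visit value untouched. This stands as a condition. It also means that two programmers could follow the SAP and report different counts.

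SAP Appendix 2 states that no protocol-planned analysis has changed, so the Protocol 9.4 count may be considered still planned. That suggests the omission was not deliberate, but it does not supply a table that the SAP's ECG section leaves out.

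The open-label gap is separate from averaging, and few ECGs are scheduled there (OLE1, OLE2 and OLE4 in Protocol 10.10). Because QTcF >500 leads to withdrawal, by-visit counts of >500 would largely equal per-participant counts if the visit value were the observed reading. That is fair for >500. It does not help for >480, which triggers no withdrawal and can recur across visits.

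No treatment decision is harmed. Withdrawal acts on the observed value, and the interim review is unblinded at individual level. Cases remain in withdrawal reasons, adverse events, the SAP listing of clinically relevant ECG abnormalities and the Protocol 9.4 listings. Few are expected: inclusion criterion 9 caps QTcF at 450 msec (men) or 470 msec (women), and Protocol 2.2.2 reports no clinically significant ECG effect in earlier studies. All of this stands and limits the matter to summary counts.

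Averaging also reduces measurement noise, and a highest single reading set against a triplicate-mean baseline is biased upwards. That is a real but small cost of the change.

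**Conclusion.** The concern holds. As written, the averaging rule can remove a participant from the by-timepoint >500 msec count if the alert repeats are stored under the visit. With the assumed readings, a first value of 512 msec leaves the category unless recovery is slower than about 2 msec per hour; a first value of 550 msec can stay or leave. One such participant is the difference between 1/40 and 0/40. The change and shift tables are affected only if their maximum is taken over visit means, which the SAP leaves open.

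The lack of an open-label ever-reached count of >480 and >500 msec depends on neither the storage nor the meaning of maximum. It follows from the SAP's wording set against Protocol 9.4.

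This is a reporting weakness and does not affect participant protection. It should be corrected because the correction is cheap. Confidence is medium, since storage is unspecified and every QTc value used here is assumed.

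**What to change.** In SAP 5.6.2.3:

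- Limit averaging to the screening triplicate and the by-visit descriptive statistics.
- Base the QTc value categories, the maximum-change table and the shift table on the highest single postbaseline QTc reading, including repeat and unscheduled ECGs. State that this is what the maximum postbaseline value means.
- Give the QTc value categories once per phase, so that the open-label phase also has the ever-reached count of Protocol 9.4.
- Leave the heart rate, PR and QRS tables as they are.

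The cost is one or two sentences of SAP text and one programming rule, with no new data. The downside is that participants with more ECGs have more chances of a high reading, compared with a baseline that is the mean of three. A footnote to the tables can say so.

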5.6.2.4. Other Safety Parameters

5.6.2.4.1. Columbia Suicide Severity Rating Scale (C-SSRS)

The C-SSRS is a low-burden measure of the spectrum of suicidal ideation and behavior that was developed to assess severity and track suicidal events through any intervention (Posner 2007). It is a clinical interview providing a summary of both suicidal ideation and behavior that can be administered during any evaluation or risk assessment to identify the level and type of suicidality present. The C-SSRS has been used frequently in clinical studies, and is a validated, standard measure for suicidal ideation assessment. Using the C-SSRS, the outcomes will be categorized using the scoring for the 11 categories:

Suicida	Suicidal Ideation (1-5)		
1	Wish to be dead		
2	Non-specific active suicidal thoughts		
3	Active suicidal ideation with any methods (not plan) without intent to act		
4	Active suicidal ideation with some intent to act, without specific plan		
5	Active suicidal ideation with specific plan and intent		
Suicida	Suicidal Behavior (6-10)		
6	Preparatory acts or behavior		
7	Aborted attempt		
8	Interrupted attempt		
9	Actual attempt		
10	Suicide		
Non-su	Non-suicidal self-injurious behavior (11)		
11	Non-suicidal self-injurious behavior		

If no events qualify for a score of 1 to 10, a score of 0 will be assigned (0="no suicidal ideation or behavior that can be assessed on the basis of C-SSRS"). A participant with a score of 11 will be considered as not having suicidal ideation or behavior.

Shifts from baseline to the maximum postbaseline score pertaining to suicidal ideation or suicidal behavior (i.e., scores 0 to 10) will be summarized by intervention for each cohort for the double-blind phase and open-label phase.

[figure not shown]
The maximum score (of scores 0 to 10) assigned to each participant will be grouped into one of three broad categories: No suicidal ideation or behavior (0), Suicidal ideation (1-5), Suicidal behavior (6-10). Shifts from the baseline to the maximum postbaseline category will be summarized by intervention for each cohort for the double-blind phase and open-label phase.

A frequency distribution of the scores for the 11 categories will be provided at each time point within each phase for each cohort.

Listings will be provided for participants with suicidal ideation/behavior at screening (lifetime recall and past 12 months recall) and also for participants with post-baseline non-suicidal self-injurious behavior during the study conduct.

